11 EXTENT OF EXPOSURE AND TREATMENT COMPLIANCE

Summaries of exposure and compliance to study drug will be provided for the Safety Analysis Set and Full Analysis Set.

11.1 Exposure to Study drug

For each subject, the duration of exposure to study drug is calculated as follows:

$$\text{Duration of exposure} = \text{last dose date} - \text{first dose date} + 1$$

Duration of exposure will be summarized descriptively as both continuous and categorical variables. For the categorical presentation, the number and percentage of subjects in each of the following categories will be displayed: <1 week (1 to 6 days), 1 to <2 weeks (7 to 13 days), 2 to <4 weeks (14 to 27 days), 4 to <6 weeks (28 to 41 days), and ≥ 6 weeks (42 days or longer). A Kaplan-Meier curve of duration of exposure will also be presented.

The pimavanserin dose levels are expressed as free base.

11.2 Measurement of Study Drug Compliance

Study drug compliance (in percentage) for a given subject is defined as follows:

$$\text{Compliance} = \left[\frac{\text{tablets dispensed} - \text{tablets returned}}{2 \times \text{duration of exposure}} \right] \times 100\%$$

Compliance will be summarized as both continuous and categorical variables. For categorical presentation, the number and percentage of subjects in each of the following categories will be presented: <80%, ≥ 80 to <120%, and $\geq 120\%$.

12 EFFICACY ANALYSES

All efficacy analyses will be performed on the Full Analysis Set.

12.1 Efficacy Variables

12.1.1 Primary Efficacy Endpoint

The primary efficacy endpoint is the change from Baseline to Week 8 in the HAMD-17 total score.

12.1.2 Secondary Efficacy Endpoints

Secondary efficacy endpoints are the following:

- Change from Baseline in HAMD-17 total score at Weeks 2, 4, and 6
- Proportion of responders (defined as $\geq 50\%$ reduction from Baseline in HAMD-17 total score)
- CGI-I score
- Change from Baseline in CGI-S
- Change from Baseline in SCOPA-NS
- Change from Baseline in SCOPA-DS
- Change from Baseline in EQ-5D-5L

12.2 Adjustment for Covariates

For continuous variables (except CGI-I) analyzed using the mixed model for repeated measures (MMRM), the Baseline value of the endpoint being analyzed will be included as a covariate as described in [Section 13](#). For CGI-I, the Baseline CGI-S score will be included as a covariate in the MMRM analysis.

12.3 Handling of Missing Data

Total scores that are missing, after any imputation of individual missing items as described in [Section 5.2.1](#), will not be imputed. Analysis of covariance (ANCOVA) and EQ-5D categorical analyses will be performed using the last observation carried forward (LOCF) method of imputation for missing data. The LOCF method will carry forward the Baseline value if necessary.

If the last dose date of study drug is missing for a subject who completed or early terminated from the study, then the date of the end-of-study/early termination visit will be used in the calculation of treatment duration. For the incomplete last dose date of the study drug, the imputation algorithms will be detailed in the ADS document. The missing or incomplete

dates will be displayed in the data listings as reported on the eCRF rather than the imputed dates.

For any data summarization that occurs before final database lock, if a subject is still ongoing, then that subject's last dose date will be imputed using the database extract date.

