- d Thyroid-stimulating hormone (TSH) will only be assessed at Screening. TSH will not be analyzed as part of the chemistry serum testing at other study visits.
- e Applicable only to women of childbearing potential. A serum pregnancy test is performed at Screening and a urine pregnancy test at Baseline and Week 8.
- f Only weight will be measured after Screening.
- g Subject terminating early should at a minimum complete assessments of safety (vital signs, ECG, AEs, clinical laboratories, C-SSRS) and, if possible, complete all Week 8 assessments.

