5.2.4 Scale for Outcomes in Parkinson's Disease (SCOPA) – Sleep Scale

The SCOPA-Sleep scale is assessed at Baseline, Week 4, and Week 8/ET visits.

The SCOPA-Sleep was developed for research in Parkinson's disease to evaluate both nighttime sleep (NS) and daytime sleepiness (DS). The SCOPA-Sleep scale consists of 3 subscales, SCOPA-NS, SCOPA-DS, and one additional question that evaluates overall sleep quality. For each subscale, the time frame is the preceding month.

The SCOPA-NS subscale addresses problems in nighttime sleep and consists of 5 items: sleep initiation, sleep fragmentation, sleep efficiency, sleep duration, and early wakening. Each item has 4 response options (ranging from 0=not at all, to 3=a lot) such that the minimum score is 0 and the maximum score is 15, with higher scores indicating more severe NS problems.

The SCOPA-DS subscale addresses problems in daytime sleepiness and consists of 6 items: how often the subject 1) fell asleep unexpectedly, 2) fell asleep peacefully, 3) fell asleep watching TV/reading, 4) fell asleep while talking to someone, 5) had difficulty staying awake, and 6) whether falling asleep in the daytime was considered a problem. Each item has 4 response options (ranging from 0=never, to 3=often). Therefore, possible SCOPA-DS subscale scores can range from 0 to 18, with higher scores indicating more severe DS problems.

If only one SCOPA-NS item is missing, then the subscale score will be imputed by replacing the missing item with the mean (rounded to the nearest integer) of the non-missing items for a given subject and timepoint. If more than 1 item is missing, then the subscale total score will remain missing. The same imputation algorithm will be applied to the SCOPA-DS subscale.

Global sleep quality is assessed using a single-item 7-point scale (1=slept very well to 7=slept very badly). This item will not be included in the SCOPA-DS or SCOPA-NS total scores. Missing values for the global sleep quality items will not be imputed.

5.2.5 EQ-5D-5L Proxy Version 1

The EQ-5D-5L questionnaire is assessed at Baseline, Week 4, and Week 8/ET.

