The EQ-5D-5L is a standardized measure of health status that provides a simple, generic measure of health for clinical and economic appraisal. In this study, Proxy Version 1 will be administered, in which the caregiver (the proxy) is asked to rate the subject's health-related quality of life in his/her (the proxy's) opinion. This questionnaire consists of 2 components – the EQ-5D-5L descriptive system and the EQ-5D-5L Visual Analogue scale (EQ-5D-5L VAS).

The descriptive system consists of 5 dimensions: mobility, self-care, usual activities, pain/discomfort, and anxiety/depression. Each dimension has 5 levels (responses): no problem (1), slight problems (2), moderate problems (3), severe problems (4), and extreme problems (5). The digits for the 5 dimensions are combined into a 5-digit code that describes the subject's health state.

The EQ-5D-5L VAS records the subject's health on a vertical visual analogue scale, where the upper endpoint is labeled "The best health you can imagine" and is numbered 100, while the lower endpoint is labeled "The worst health you can imagine" and is numbered 0. The EQ-5D-5L VAS will be treated as a continuous endpoint.

Missing values will not be imputed for either the descriptive system or EQ-5D-5L VAS.

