13.1.9 EQ-5D-5L

13.1.9.1 EQ-5D-5L Descriptive System

For each EQ-5D-5L dimension the proportion of subjects reporting no, slight, moderate, severe, and extreme/unable to perform activity will be summarized descriptively at each timepoint (Baseline, Week 4, and Week 8), using both OC and LOCF analysis methods.

Change from Baseline in EQ-5D-5L health state will be assessed with the Pareto classification of health change (PCHC) method. By using this methodology, at each post-Baseline visit (Week 4 and Week 8), each EQ-5D-5L health state will be classified into one of four categories, relative to the Baseline health state:

- Improved = improved on at least one dimension and not worsened on any other dimension
- Mixed = improved on at least one dimension and worsened on at least one other dimension
- No change = no changes in any dimension
- Worsened = deterioration on at least one dimension and no improvement on any other dimension

The proportion of subjects in each PCHC category will be summarized descriptively at Week 4 and Week 8, using both OC and LOCF analysis methods.

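### In the LOCF version of the EQ-5D-5L health-change table, a subject with no post-Baseline EQ-5D is 'No change' by construction, and SAP 5.2.5 conflicts with the use of LOCF there

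*SAP*

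**What the plan says.** SAP 12.3 states: "Analysis of covariance (ANCOVA) and EQ-5D categorical analyses will be performed using the last observation carried forward (LOCF) method of imputation for missing data". It then adds: "The LOCF method will carry forward the Baseline value if necessary".

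SAP 13.1.9.1 compares each subject's Week 4 and Week 8 health state with the Baseline state and assigns one of four PCHC classes: 'Improved', 'Mixed', 'No change' or 'Worsened'. Two of the definitions matter here: "No change = no changes in any dimension" and "Worsened = deterioration on at least one dimension and no improvement on any other dimension". On reporting it says: "The proportion of subjects in each PCHC category will be summarized descriptively at Week 4 and Week 8, using both OC and LOCF analysis methods".

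On collection, SAP 5.2.5 says: "The EQ-5D-5L questionnaire is assessed at Baseline, Week 4, and Week 8/ET". The early-termination note to Protocol Table S-1 reads "Subject terminating early should at a minimum complete assessments of safety". It lists safety items that do not include EQ-5D, then asks for all the Week 8 assessments where possible.

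The Full Analysis Set (SAP 4.2) requires a Baseline and at least one post-Baseline HAMD-17 total score. It has no EQ-5D requirement.

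SAP 5.2.5 also states: "Missing values will not be imputed for either the descriptive system or EQ-5D-5L VAS".

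**The concern.** PCHC measures change from Baseline. When the value carried forward is Baseline itself, the class follows from the imputation rule and tells the reader nothing about the subject's health at that visit. The LOCF table would combine subjects who were assessed and found unchanged with subjects who were never reassessed. SAP 13.1.9.1 asks for no row or count that separates the two groups.

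Such subjects can exist. HAMD-17 is collected at Week 2, but EQ-5D is not scheduled again until Week 4. Week 4 is the more exposed visit: unless an EQ-5D was obtained earlier at an early-termination or unscheduled visit, the only value available to carry into Week 4 is Baseline. A subject who misses only the Week 4 EQ-5D and completes Week 8 is therefore also 'No change' at Week 4.

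This is a single-arm study, so the class percentages are read on their own, with no control arm sharing the distortion. There is also a plain inconsistency: 5.2.5 says the descriptive system is not imputed, while 12.3 and 13.1.9.1 impute it.

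**Working it through.** **The plan's own figures.** The documents give no figure for EQ-5D or PCHC. The sample-size figures (SAP 3.5) serve here only to set a plausible range. With a mean reduction of 3, SD 6 and two-sided alpha 0.05, the paired t-test has power 0.808 at n = 34 and 0.795 at n = 33, so 34 is the minimum for 80%. Inflating for 15% non-evaluable gives 34/0.85 = 40. Both stated figures reproduce. Fifteen per cent of 40 is 6, used below as an assumed upper end for affected subjects. It is not a bound set by the documents.

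**Step 1: the class assigned when Baseline is carried forward.** The descriptive system has 5 dimensions with 5 levels each, so 5^5 = 3,125 possible states. Applying the four PCHC rules with the post-Baseline state set equal to Baseline puts 3,125 of 3,125 in 'No change' and none in the other classes.

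**Step 2: effect on the percentages.** Let N be the subjects in the LOCF table, k those with Baseline carried forward, and p the proportion in a class among the N − k assessed.

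- 'No change' under LOCF = [p(N − k) + k]/N
- any other class under LOCF = p(N − k)/N

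Each affected subject adds 1/N to 'No change' before dilution and (1 − p)/N after it. With N = 40 and p = 0.20, that is 1/40 = 2.5 points gross and 0.80/40 = 2.0 points net.

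**Step 3: range over k.** Assumed: N = 40; among those assessed, 40% 'Improved' and 20% in each other class. These are proportions, so the implied counts need not be whole numbers.

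| k | No change | Worsened | Mixed | Improved |
|---|---|---|---|---|
| 0 | 20.0% | 20.0% | 20.0% | 40.0% |
| 1 | 22.0% | 19.5% | 19.5% | 39.0% |
| 3 | 26.0% | 18.5% | 18.5% | 37.0% |
| 6 | 32.0% | 17.0% | 17.0% | 34.0% |

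For k = 6: (0.20 × 34 + 6)/40 = 32.0%; 0.20 × 34/40 = 17.0%; 0.40 × 34/40 = 34.0%. The observed-cases table stays at the k = 0 row for every k.

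**Step 4: direction.** If all six unseen subjects had worsened, 'Worsened' would be (0.20 × 34 + 6)/40 = 32.0%, against 17.0% under LOCF. If all six had improved, 'Improved' would be (0.40 × 34 + 6)/40 = 49.0%, against 34.0%. The rule can err either way.

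**Step 5: a whole-number example.** Assume 38 in the Full Analysis Set, of whom 34 are assessed (6 'No change', 6 'Worsened', 22 'Improved' or 'Mixed') and 4 have no post-Baseline EQ-5D.

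- 'No change': 6/34 = 17.6% becomes (6 + 4)/38 = 26.3%.
- 'Worsened': 6/34 = 17.6% becomes 6/38 = 15.8%, a fall of 1.9 points.
- 'Improved' plus 'Mixed': 22/34 = 64.7% becomes 22/38 = 57.9%, a fall of 6.8 points.

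In this example the larger loss falls on 'Improved' and 'Mixed' combined.

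**The case against.** The strongest reply is that the rule is stated in advance, the table is labelled LOCF, and the observed-cases version that must accompany it leaves these subjects out. A reader can compare the two. That stands. It means the undiluted percentages are available, and nothing in the SAP calls an imputed class measured. It does not make the LOCF version informative, because imputed and observed 'No change' remain mixed there.

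A reader might infer that the rule hides deterioration, since an affected subject can never be 'Worsened'. The documents do not support so one-sided a reading: the same subject can never be 'Improved' or 'Mixed' either, and nothing in the documents says that subjects without a later EQ-5D did worse.

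A reader might also see a clash with the HAMD-17 and CGI-I responder rules (SAP 13.1.5 and 13.1.7), which count missing as non-response or not improved. That contrast is weak. Carrying Baseline forward also counts the subject as not improved, and neither responder rule counts a missing subject as worsened.

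Nor is everyone who stops after Week 2 affected. The schedule asks for the Week 8 assessments at early termination where possible, the protocol's withdrawal text calls for reasonable efforts to complete them, and SAP 5.3.1 admits early-termination assessments to the analyses. A state obtained that way is post-Baseline and could be carried forward. The SAP does not say how an EQ-5D falling in the Week 2 or Week 6 window is used.

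Finally, 5.2.5 could be read as a scoring rule for items within one assessment, with 12.3 governing missed visits. That would remove the conflict, but 5.2.5 does not limit itself in that way.

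**Conclusion.** The point holds as a small improvement to a descriptive secondary summary. What is certain is the mechanism: under SAP 12.3 and 13.1.9.1, a Full Analysis Set subject with a Baseline EQ-5D and no post-Baseline EQ-5D by the visit is 'No change' in the LOCF table whatever happened to that subject. 'No change' is inflated relative to observed cases and the other three classes are diluted, unless every assessed subject is already 'No change'.

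The size is not known. It rests on the assumed 0 to 6 affected subjects out of 40 and on the assumed class mix; on those assumptions the shift in 'No change' runs from 0 to 12 percentage points. The count could be zero, and at Week 4 it also includes subjects who missed only that assessment. No net direction of bias can be claimed.

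PCHC carries no hypothesis test. The HAMD-17 MMRM, the significance level, power and sample size are untouched. The conflict between SAP 5.2.5 and the two LOCF sections needs no assumption about numbers and should be reconciled in any case.

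**What to change.** In SAP 12.3 and 13.1.9.1, state that for the PCHC table only post-Baseline EQ-5D states are carried forward. Show subjects with none by the given visit in a separate 'No post-Baseline assessment' row, within the same denominator. In the whole-number example that row would hold 4/38 = 10.5%, with 'No change' 6/38 = 15.8%, 'Worsened' 6/38 = 15.8%, and 'Improved' plus 'Mixed' 22/38 = 57.9%.

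Amend SAP 5.2.5 so that it agrees with these sections, for instance by limiting its no-imputation statement to values within a single assessment and pointing to 12.3 for missed visits.

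The cost is one or two sentences and one extra table row; the LOCF table would also no longer assign every subject to a PCHC class. No protocol amendment appears necessary: Protocol 9.8.2 asks for LOCF only in the paired t-tests of continuous endpoints and does not mention PCHC.

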12.4 Multiple Comparisons / Multiplicity

No adjustments of p-values for multiple comparisons will be performed.

12.5 Examination of Subgroups

The MMRM analysis described in Section 13.1.1 will be performed separately for the primary efficacy variable (HAMD-17 total score), and for CGI-S and CGI-I as described in [Section 13.1.6](#) and [Section 13.1.7](#), respectively, for each of the following subgroups:

- treatment regimen (pimavanserin monotherapy or pimavanserin adjunctive therapy)
- age group (<70 or \geq 70 years old)
- sex (male or female)
- primary race (white or non-white)
- Baseline symptom severity measured by HAMD-17 total score (<24 or \geq 24)

The LS mean changes with corresponding 95% CIs from the subgroups will also be graphically presented in forest plots for the above efficacy variables.

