### **4.2 Inclusion Criteria**

1. Is a male or female  $\geq 50$  years of age
2. Can understand and provide signed informed consent, request for medical records and/or subject privacy form if applicable according to local regulations [REDACTED]  
[REDACTED] can be reliably rated on assessment scales (in the opinion of the Investigator), and has a reliable [REDACTED] (personal friend, or professional caregiver) who can report on the subject's health-related quality of life
4. Has a clinical diagnosis of idiopathic Parkinson's disease with a minimum duration of 1 year, defined as the presence of at least three of the following cardinal features, in the absence of alternative explanations or atypical features:
  - a. rest tremor
  - b. rigidity
  - c. bradykinesia and/or akinesia

- d. postural and gait abnormalities
- 5. Meets clinical criteria for depression with Parkinson's disease as listed in the NINDS/NIMH Guidelines ([Marsh et al. 2006](#))
- 6. Has a Hamilton Depression Scale-17 item (HAM-D-17) total score  $\geq 15$  at Screening and Baseline
- 7. If currently taking an antidepressant, is being treated with only one of the following SSRI or SNRI antidepressants at a dose within the United States Food and Drug Administration (US FDA)-approved dose range. Subjects who are currently taking a second antidepressant or antidepressant augmentation agent at a sub-therapeutic dose or for an inadequate duration at Screening, and can be discontinued from this agent before the Baseline visit (in the opinion of the Investigator), may be eligible for the study.
  - a. Citalopram
  - b. Escitalopram
  - c. Paroxetine
  - d. Fluoxetine
  - e. Sertraline
  - f. Vortioxetine
  - g. Duloxetine
  - h. Venlafaxine
  - i. Desvenlafaxine
  - j. Venlafaxine XR
  - k. Vilazodone
  - l. Levomilnacipran

Current or previous treatment with an antidepressant is not required [REDACTED]  
[REDACTED] appropriate (e.g.,  
symptoms are not well controlled or the subject cannot tolerate the [REDACTED]  
[REDACTED]

- 8. If the subject is currently taking an antidepressant and has an improvement in depression of less than 75% when working at its best, as confirmed by the Massachusetts General Hospital Antidepressant Treatment Questionnaire (MGH ATRQ)
- 9. Has a Mini Mental State Exam (MMSE) score  $\geq 21$
- 10. Is on a stable dose of anti-Parkinson's medication for at least 1 month prior to Screening

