5.2.1 Hamilton Depression Rating Scale 17-Items (HAMD-17)

The HAMD-17 is assessed at Screening, Baseline, Weeks 2, 4, 6, and Week 8/ET visits.

The HAMD-17 is a 17-item clinician-administered questionnaire used to provide an indication of depression, and as a guide to evaluate recovery (Hamilton, 1960). The

questionnaire assesses symptoms over the past week (7 days). The questionnaire is designed for adults to rate the severity of, and change in, depressive symptoms by probing mood, feelings of guilt, suicide ideation, insomnia, agitation or retardation, anxiety, weight loss, and somatic symptoms. Each item on the questionnaire is scored on a 3- or 5-point scale, depending on the item, and the total score is compared to the corresponding descriptor. The HAMD-17 total score can range from a minimum of 0 to a maximum of 52. A score of 0-7 is considered normal. Scores of 14 or higher indicate moderate, severe, or very severe depression.

If more than 3 items are missing, the total score will be set to missing. If 3 or fewer items are missing, then missing items will be imputed as follows:

- Items using a 3-point scale (4, 5, 6, 12, 13, 14, 16, and 17): missing values will be imputed using the arithmetic mean of the non-missing items that are also scored on a 3-point scale, then rounded to the nearest integer
- Items using a 5-point scale (1, 2, 3, 7, 8, 9, 10, 11, and 15): missing values will be imputed using the arithmetic mean of the non-missing items that are also scored on a 5-point scale, then rounded to the nearest integer

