5.3 Analysis Visit Windows

Baseline will be defined as the last non-missing result, including results from repeated and unscheduled measurements, before dosing.

Efficacy and safety assessments will be summarized by analysis visit as shown in [Table 2](#) below.

Table 2 Analysis Visit Windows

Analysis Visit Name	Study Visit	Target Study Day ¹	Study Day Interval
Baseline	Visit 2 (Baseline)	1	≤ 1
Week 2	Visit 3 (Week 2)	15	2 to 21
Week 4	Visit 4 (Week 4)	29	22 to 35
Week 6	Visit 5 (Week 6)	43	36 to 49
Week 8	Visit 6 (Week 8/ET)	57	50 to 63
Follow-up	Visit 7 (Week 10/Safety Follow-up)	71	≥ 64

¹ Study day = assessment date - first dose date + 1 if the assessment date \geq first dose date, otherwise study day = assessment date - first dose date. Study day 1 is the day of first administration of study drug (pimavanserin).

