13.1.1 Primary Analysis using MMRM in the Full Analysis Set

The HAMD-17 total score will be analyzed using mixed model repeated measures (MMRM) in the Full Analysis Set. The dependent variable will be the change from Baseline in the

HAMD-17 total score. The independent variables in the model will include the following: visit (Week 2, Week 4, Week 6, and Week 8), Baseline-by-visit interaction, and the Baseline HAMD-17 total score as a continuous covariate. An unstructured covariance matrix will be used and the Kenward-Roger approximation will be used to adjust the denominator degrees of freedom. Least squares (LS) adjusted means will be estimated using observed cases (OC).

In the event that the model fails to converge using the unstructured covariance matrix, then the following covariance structures will be modeled in the order given: heterogeneous Toeplitz, heterogeneous compound symmetry, heterogeneous autoregressive(1), Toeplitz, compound symmetry, autoregressive(1), variance components. The first covariance structure that allows for convergence will be selected for the final model.

Summary statistics for the HAMD-17 total score (observed and change from Baseline) will be presented for all visits from Baseline through Week 8. For change from Baseline values at each post-Baseline visit, LS means and standard errors (SE), the corresponding 95% confidence interval and p-value will also be presented. In addition, LS mean \pm SE over time for the change from Baseline values will also be presented in line plots.

The hypothesis testing will be performed based on the LS mean change at Week 8 and will be tested at an alpha level of 0.05 (2-sided).

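### The Baseline severity split in SAP 12.5 builds regression to the mean into the HAMD-17 forest plot, in favour of the >=24 group

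*SAP*

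**What the plan says.** SAP 12.5 lists five subgroup factors. One is "Baseline symptom severity measured by HAMD-17 total score", cut at 24. The primary MMRM "will be performed separately for the primary efficacy variable (HAMD-17 total score") in each subgroup, and also for CGI-S and CGI-I. On display it says: "The LS mean changes with corresponding 95% CIs from the subgroups will also be graphically presented in forest plots".

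The model comes from SAP 13.1.1. On the outcome it says "The dependent variable will be the change from Baseline in the" HAMD-17 total score. Baseline enters with its visit interaction, the "HAMD-17 total score as a continuous covariate". SAP 5.3 makes Baseline a single value: "Baseline will be defined as the last non-missing result, including results from repeated and unscheduled measurements, before dosing".

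A second pre-treatment score exists. SAP 5.2.1 states: "The HAMD-17 is assessed at Screening, Baseline, Weeks 2, 4, 6, and Week 8/ET visits". Protocol 4.2 requires a total of at least 15 "at Screening and Baseline".

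The design is single-arm (SAP 3.1, Protocol 9.5). Neither document gives a HAMD-17 reliability, a Baseline mean or SD, a common Baseline value for the subgroup LS means, an interaction model, or a caution about regression to the mean.

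**The concern.** The score that assigns a subject to a severity group is also the score from which that subject's change is measured. Some subjects reach 24 because their Baseline rating happened to be high that day. That part of the score is not expected to recur at Weeks 2 to 8, so they appear to improve whatever the drug does. The reverse applies below 24, partly offset by the entry threshold.

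A control arm would normally cancel this, because both arms of a severity stratum regress alike. Here there is none. The Baseline covariate does not remove it either: with separate fits and no common reference value, each LS mean is by default taken at its own subgroup's mean Baseline, which leaves the difference in place.

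At stake is a prespecified plot that tends to show greater benefit in more severe subjects even if the drug does nothing, or acts equally in both groups.

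**Working it through.** **The plan's own figure.** SAP 3.5 assumes a 3-point mean reduction, SD 6.0 and a two-sided 0.05 paired t-test. By the noncentral t, power is 79.5% at n = 33 and 80.8% at n = 34, and 34/0.85 = 40. Both stated numbers reproduce. They size the overall test; the documents give no figure for a severity contrast.

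**Model for the artefact.** Score = stable true level + independent error at each visit, with no true change and no drug effect. With reliability r, expected change given Baseline is about −(1 − r) × (Baseline − population mean), so

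gap between groups ≈ (1 − r) × (mean Baseline in >=24 − mean Baseline in <24).

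**Inputs from the documents:** cut at 24; entry at 15 or more at Screening and Baseline; SD of change 6.0; 34 evaluable.

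**Inputs assumed:** before the entry rule, Baseline mean 15 to 22 and SD 3 to 6; r from 0.5 to 0.9. Only scenarios with 10% to 50% of enrolled subjects at >=24 were kept. The planned SD of 6.0 does not fix r, because it also contains true differences in response.

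**Simulated spurious extra fall in the >=24 group** (integer scores, both entry rules; gap in mean Baseline 4.9 to 8.2 points):

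| Assumed r | Spurious gap (points) |
|---|---|
| 0.9 | 0.5 to 1.1 |
| 0.8 | 1.0 to 2.0 |
| 0.7 | 1.5 to 2.9 |
| 0.6 | 2.0 to 3.7 |
| 0.5 | 2.5 to 4.4 |

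The formula agrees: 0.1 × 4.9 = 0.5 at the low end and 0.5 × 8.2 = 4.1 at the high end. Simulation runs slightly above it because the Screening entry rule raises the true level of the lower group. The direction was the same in every scenario.

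**One scenario in full** (mean 20, SD 4, r = 0.6). Separate models at their own mean Baselines give +0.4 (<24) and −2.3 (>=24), a gap of 2.7 with no drug effect. Evaluated at the overall mean Baseline, the same models give −0.26 and −0.33, a gap of 0.07. One model with continuous Baseline plus a subgroup term gives a gap of about 0.1.

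**Precision.** With SD 6.0 and n = 34, the standard error of the subgroup difference is 6 × √(1/5.1 + 1/28.9) = 2.9 with 15% at >=24, and 6 × √(1/13.6 + 1/20.4) = 2.1 with 40%.

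**Candidate remedies**, in a narrower assumed set: true mean 16 to 20, between-subject SD 4 to 4.5, error SD 2.5 to 3.5. This implies r from 16/(16 + 12.25) = 0.57 to 20.25/(20.25 + 6.25) = 0.76. Screening and Baseline errors were taken as independent or correlated at 0.5, with Week 8 error independent.

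| Grouping and evaluation | Spurious gap (points) |
|---|---|
| Baseline split, own mean Baselines (as planned) | 1.8 to 3.7, favours >=24 |
| Baseline split, common Baseline or one model with subgroup term | about 0 to 0.3, either direction |
| Screening split, own mean Baselines, independent errors | 0.3 to 0.9, favours <24 |
| Screening split, own mean Baselines, errors correlated 0.5 | 0.5 to 1.2, favours >=24 |
| Screening split at a common Baseline | 1.6 to 2.7, favours <24 |

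The last row fails for a simple reason. Of two subjects with the same Baseline score, the one with the higher Screening score probably has the higher true level, so that subject's Baseline is more likely to be an underestimate.

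**The case against.** The strongest reply is that this is an exploratory display. SAP 12.5 plans within-group LS means and intervals, with no test between severity groups and no claim of a differential effect. Protocol 9.6 names only treatment regimen as a subgroup; severity is added in the SAP. All of that is correct and limits the point to the contrast. It does not dispose of it, since rows placed side by side in a forest plot invite comparison.

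A second reply is that noise will dominate. In the narrower assumed set about 4 to 12 of 34 subjects fall at >=24, and the standard error of the difference is 2.1 to 2.9 points. So one trial this small need not show the pattern. But the bias has a fixed direction, can be as large as the standard error, and is not reflected in the intervals.

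A third reply concerns the Screening split. It is not clean if rating errors persist over the up to 3 weeks between visits. Protocol 3.2 also lets a second antidepressant or augmentation agent be stopped before Baseline, so a Screening score may precede a real change in state. Both points stand and belong among the costs.

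A reader might also infer a definite bias of 2 to 3.6 points, about the size of the 3-point target. The documents do not support a range that narrow: it corresponds to a reliability near 0.6, which they do not state. At 0.9 the gap is only 0.5 to 1.1.

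**Conclusion.** The concern holds for the HAMD-17 severity contrast. As planned, that contrast includes regression to the mean favouring the >=24 group, by about 0.5 to 4.4 points for an assumed reliability of 0.9 to 0.5 and the assumed Baseline distributions above. The direction rests on the design; the size rests on those assumptions. The contrast cannot be read as a differential drug effect.

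A reader might go further and conclude that the subgroup results cannot be interpreted at all, or that the main result is compromised. Neither follows from this split. The primary MMRM at Week 8 does not use it, and the other four subgroup factors are not cut on the HAMD-17 score. The computed gap also does not apply to the CGI-S and CGI-I rows, which are not measured from Baseline HAMD-17; no figure was derived for them. This is a worthwhile correction to an exploratory display.

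**What to change.** Amend SAP 12.5 for the HAMD-17 severity rows, choosing one route:

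- **Screening split.** Group by Screening HAMD-17 (<24 or >=24). Keep Baseline as reference and covariate, and each LS mean at its own subgroup's mean Baseline.
- **Baseline split, common reference.** Keep the planned groups, but fit one MMRM with continuous Baseline plus a subgroup term, or evaluate both LS means at a common Baseline.

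Do not combine the Screening split with a common-Baseline evaluation, which creates a spurious gap of about 1.6 to 2.7 points the other way.

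Add a footnote that some regression to the mean may remain, from the Baseline entry threshold of 15 and from any error shared between Screening and Baseline.

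Cost: a short SAP edit and a changed grouping variable or model statement, with no new data, since every enrolled subject should have a Screening score. The Screening route classifies severity on a value up to 3 weeks old, and under the narrower assumed inputs about 25% to 64% of its >=24 group would have Baseline below 24, so the row label must change. The common-Baseline route leaves the smaller artefact in simulation but extrapolates, because the two groups do not overlap on Baseline.
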